5.4 Lifestyle Considerations

No restrictions are required.

5.5 Screen Failures

Screen failures are defined as participants who consent to participate in the clinical study but are not subsequently randomly assigned to study intervention. A minimal set of screen failure information is required to ensure transparent reporting of screen failure participants to meet the Consolidated Standards of Reporting Trials publishing requirements and to respond to queries from regulatory authorities. Minimal information includes demography and reason for screen failure (e.g., eligibility requirements failed).

Individuals who do not meet the criteria for participation in this study (screen failure) may not be rescreened.

5.5.1 Screening and Enrollment Log and Participant Identification Numbers

The participant's enrollment will be recorded in the Screening and Enrollment Log.

Upon enrollment, each participant will receive a unique participant identification number. Participant numbers must not be re-used for different participants.

6 Study Intervention

Study intervention is defined as any investigational intervention(s), marketed product(s), placebo, or medical device(s) intended to be administered to a study participant according to the study protocol.

6.1 Study Intervention Administered

Table 6-1 Study Intervention(s) Administered

[figure not shown]
Study Treatment	RESP301 + SOC
Intervention Name:	RESP301
Type:	Drug
Dosage Formulation:	Admixture for inhalation
Unit Dose Strength(s):	Delivered dose (62 mg) sodium nitrite (NaNO ₂) (6 mL of NO-generating admixture of 150 mM NaNO ₂ , 50 mM mannitol and 100 mM citric acid)
Dosage Level(s):	One 6 mL-inhalation TID (every 8 hours) with at least 6 hours between 2 consecutive doses.
Route of Administration:	Inhalation
IMP and NIMP:	IMP
Sourcing:	RESP301 provided centrally by the Sponsor.
Dosing Instructions:	A vibrating mesh nebulizer will be used to administer the RESP301, under the direction of the study physician. Treatment is to commence within 5 minutes of RESP301 preparation. For the first 10 participants (up to the first IDMC safety review) RESP301 will be administered by intermittent inhalation to monitor tolerability and response to RESP301. After reviewing safety data, the IDMC will decide whether the intermittent inhalation of RESP301 can be replaced by a continuous inhalation. Before initiating each RESP301 inhalation, supplemental oxygen will be interrupted for a few minutes until SpO ₂ levels are stable. Depending on the extent of SpO ₂ decrease, the RESP301 inhalation may be initiated or supplemental oxygen may be resumed at the discretion of the investigator. After treatment initiation, in case of SpO ₂ decrease, RESP301 inhalation may be paused and supplemental oxygen resumed. If the participant is unable to tolerate nebulization without supplemental oxygen, nasal oxygen may be administered during nebulization.
Packaging and Labeling:	Study intervention will be provided as two separate vials: NaNO ₂ /mannitol (3 mL) and citric acid buffered to pH 5.4 (3 mL), which will be labeled as required per country requirement.

Staggered dosing approach for the first 10 participants:

For the first 10 participants treated before the first IDMC safety review (Section 9.6), RESP301 dose will be administered in a staggered approach: after 2 minutes of inhalation, treatment is

briefly paused to assess the participant. Provided there is no evidence of bronchospasm, treatment is continued for a further 2 minutes, after which treatment is again briefly paused for participant assessment. Thereafter, provided there is no evidence of bronchospasm and the participant is able to continue, the dose is completed (Figure 6–1), so that treatment can be quickly adjusted and rescue bronchodilator initiated if needed (Section 6.5.1). After reviewing safety data, the IDMC will decide whether the intermittent inhalation of RESP301 can be replaced by a continuous inhalation.

Figure 6–1: Staggered Dosing Approach for the First 10 Participants

6.1.1 Medical Devices

1. Medical device (not manufactured by or for Thirty Respiratory Limited) provided for use in this study will be an FDA-approved and CE marked vibrating mesh nebulizer.
2. Instructions for medical device use will be provided in the User Manual.

6.1.2 Device Training

Training will be provided to ensure all study staff are familiar with the device, including mixing the solutions, adding the admixture to the device and cleaning the device.

6.2 Preparation, Handling, Storage, and Accountability

6.2.1 Preparation of Study Intervention Product

RESP301 is prepared at bedside by mixing two sterile 3 mL solutions (one of NaNO₂/mannitol and one of citric acid buffered to pH 5.4). The solution is to be nebulized immediately or within

5 minutes post mixing as per the instructions given in the SoA (Table 1-1) and, for the first 10 participants, as in Section 6.1 above (staggered dosing). The first administration of study intervention should be provided under medical supervision.

RESP301 is mixed in the nebulizer chamber before use following the steps below (see Table 6-2 for details of composition):

1. First the vial marked A (NaNO₂ and mannitol) is opened and its contents are poured into the nebulizer chamber.
2. Next, the vial marked B (citric acid) is opened and its contents are poured into the nebulizer chamber.
3. The nebulizer lid should be closed, and the nebulizer should be swirled gently for a few seconds to mix the two solutions. The nebulizer should not be inverted.

The inhalation of the medication should start within 5 minutes of mixing the solutions and the inhalation process should be complete within 20 minutes of starting of inhalation.

This combined mildly acidified nitrite solution (6 mL) is inhaled through the mouth using a vibrating mesh nebulizer under the direction of a physician. The purpose of the acidified nitrite aerosol is to deliver NO to the participant. The delivered dose of RESP301, assessed via simulated tidal breathing is estimated to be ~40% of the masses listed below; it should be noted that delivered dose can be further affected by participant's breathing pattern and inspiratory capacity and so inter- and intra-participant variation in actual doses of these ingredients may vary, given the acute nature and high disease burden in this proposed clinical setting.

Table 6-2 Composition of Drug Product, Diluent and Admixture

	Material	Function	Quantity per vial
Drug Product	Sodium Nitrite	Drug Substance	62.10 mg
	Mannitol	Excipient	54.66 mg
	Sterile water for injection	Diluent	
	Total Volume		3.0 mL
Diluent	Citric Acid	Diluent	115.28 mg
	Sterile water for injection	Diluent	
	Total Volume		3.0 mL
Acidified Drug Product Mixture (RESP301)	Sodium Nitrite	Drug Substance	62.10 mg
	Mannitol	Excipient	54.66 mg
	Citric Acid	Diluent	115.28 mg
	Sterile water for injection	Diluent	
	Total Volume		6.0 mL

6.2.2 Storage and Accountability of Study Intervention

The Investigator or designee must document whether appropriate temperature conditions (<25°C) have been maintained during transit for all study intervention received and any discrepancies are reported and resolved before use of the study intervention.

Only participants enrolled in the study may receive study intervention and only authorized site staff may supply or administer study intervention. All study interventions must be stored in a secure, environmentally controlled, and monitored (manual or automated) area in accordance with the labeled storage conditions with access limited to the Investigator and authorized site staff.

The investigator, institution, or the head of the medical institution (where applicable) is responsible for study intervention accountability, reconciliation, and record maintenance (e.g., receipt, reconciliation, and final disposition records).

Further guidance and information for the final disposition of unused study intervention are provided in the Investigator Manual.

6.3 Measures to Minimize Bias: Randomization and Blinding

This is an open-label study; however, the specific intervention to be taken by a participant will be assigned using an interactive voice response system (IVRS)/interactive web response system (IWRS). The site will contact the IVRS/IWRS prior to the start of study intervention

administration for each participant. The site will record the intervention assignment on the applicable case report form (CRF), if required.

Potential bias will be reduced using a central stratified randomization to assign participants into one of the study treatment arms, RESP301+SOC or SOC (control), with a randomization ratio of 2:1. Participants will be stratified by country and presence of risk factors for severe outcomes of COVID-19, based on comorbidities and age as follows:

1. Age >65 years
2. Ongoing or currently treated diabetes mellitus
3. Ongoing or currently treated hypertension
4. Ongoing or currently treated cardiovascular disease
5. Ongoing or currently treated chronic lung disease
6. Cancer history of less than 3 years, basal cell skin carcinoma excluded
7. Ongoing or currently treated chronic kidney disease

Participants will be stratified as no risk factor (none of the above criteria), one risk factor (one single of the above) or high-risk factor (2 or more of the above).

6.4 Study Intervention Compliance

Participants will receive study intervention directly from the Investigator or designee, under medical supervision. The date and time of each inhalation will be recorded in the source documents and recorded in the CRF. The study participant identification will be confirmed at the time of dosing by a member of the study site staff other than the person administering the study intervention.

6.5 Concomitant Therapy

During the study, participants will receive institutional SOC for the treatment of COVID-19.

Any medication or vaccine (including over-the-counter or prescription medicines, vitamins, and/or herbal supplements) that the participant is receiving at the time of enrollment or receives during the study must be recorded along with:

- Reason for use
- Dates of administration including start and end dates
- Dosage information including dose and frequency and route

The Medical Monitor should be contacted if there are any questions regarding concomitant or prior therapy.

6.5.1 Rescue Medication

For participants treated before the first safety review by the IDMC (Section 9.6), at the time of RESP301 treatment, a ready-to-use nebulization of a bronchodilator (short acting beta agonist such as salbutamol/albuterol according to investigational site standard practice for acute bronchospasm) may be administered to participants in case of bronchospasm.

After reviewing safety data, the IDMC will decide whether the availability of rescue bronchodilator at the time of RESP301 treatment is still required.

Although the use of rescue medications is allowable for the first 10 participants, the use of rescue medication should be delayed, if possible, for at least 2 minutes following each administration of study intervention. The date and time of rescue medication administration as well as the name of the rescue medication must be recorded.

6.6 Intervention After the End of the Study

After the end of the study, participants may continue their SOC (if any). Study intervention for COVID-19 will not continue beyond this study.

7 Discontinuation of Study Intervention and Participant Discontinuation

7.1 Permanent Discontinuation of Study Intervention

It may be necessary for a participant to permanently discontinue (definitive discontinuation) study intervention. If study intervention is definitively discontinued, the participant will remain in the study to be evaluated for the Day 14 and Day 28 safety follow-ups. See the SoA (Table 1-1) for data to be collected at the time of discontinuation of study intervention and follow-up and for any further evaluations that need to be completed.

Study intervention will be permanently discontinued prior to 10 days if the participant:

- Improves to level 1 or 2 of the modified WHO ordinal scale;
- Progresses to a level > 4 of the modified WHO ordinal scale.

Additionally, study intervention should be permanently discontinued in the following circumstances:

1. Discontinuation of study intervention for abnormal liver tests should be considered if the Investigator believes that it is in best interest of the participant.
2. If, as part of normal clinical follow-up, a clinically significant change in ECG is identified, the Investigators should exercise their clinical judgement to decide whether continuing study intervention administration is in the best interest of safety of the participant.
3. AE/SAE if the Investigator believes that it is in best interest of the participant, including the following:
 - Development of significant bronchospasm * or worsening of cough that is not tolerated by the participant and leads to immediate discontinuation of the nebulization.
 - Progressive COVID-19 requiring initiation of non-invasive or invasive ventilation or high flow oxygen.
 - Development of mHb level above 3%.
 - Inability to safely continue receiving study intervention due to compromised respiratory status while off supplemental oxygen and receiving nebulized therapy (manifest by drop in SpO₂, increased respiratory rate or clinical other findings).

Refer to the SoA (Table 1-1) for data to be collected at the time of study intervention discontinuation and follow-up and for any further evaluations that need to be completed.

** Inhaled citric acid and inhaled mannitol provoke bronchospasm in patients with bronchial hyperresponsiveness in a dose dependent pattern. Although the concentrations of mannitol and citric acid are below the provocative dose and concentration inducing bronchospasm, there is a theoretical risk that a participant may develop acute bronchospasm during the use of RESP301. Participants should therefore be monitored during RESP301 administration. In case of clinical intolerance or saturation decrease, nebulization should be immediately discontinued (see Section 7.2). Further clarification of the differences in signs and symptoms for acute bronchospasm and COVID-19 progression are provided in Table 7-1.*

Table 7-1 Differences in Signs and Symptoms for Acute Bronchospasm and COVID-19 Progression

	Acute bronchospasm related to inhaled bronchial irritant	Progression of COVID-19 lung disease to acute respiratory failure
Mechanism	Acute contraction of bronchial muscles resulting in bronchial obstruction resulting in increased ventilatory load	Cytokine storm resulting in alveolar damage resulting in gas transfer impairment
Onset	Within minutes (<15 minutes) following inhalation (no late phase since it is not an allergic IgE mediated reaction)	Within hours or days and not related to nebulization
Clinical auscultatory signs	Wheezing (almost all cases)	Bilateral rales (inconstant)
Patient history	Asthma or respiratory allergy	Age > 65 years, increased BMI, high blood pressure, cardiac diseases, etc.
Reversibility with inhaled beta mimetics	Within minutes	No

Abbreviations: BMI=body mass index; IgE=immunoglobulin E.

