9.4.5.1 Adverse Events

Adverse Events will be coded using the MedDRA coding dictionary.

The number and percentage of participants with any AE, any related AE, any SAE, any related SAE, any severe AE, and related severe AE as well as the total number of events for each category will be summarized. The number of deaths due to an AE, hospitalization due to an AE, and study discontinuation due to an AE will be summarized.

The number and percentage of participants with an AE, as well as the total number of AEs, will be summarized by SOC and preferred term. This tabulation will be repeated for related AEs, SAEs, related SAEs, severe AEs, and related severe AEs.

All AEs will be provided in patient listings. Patient listings of AEs causing discontinuation of study medication, AEs leading to death, SAEs, related AEs, and severe AEs will be produced.

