10.4.1 Definition of AE

AE Definition

• An AE is any untoward medical occurrence in a patient or clinical study participant, temporally associated with the use of a study intervention, whether or not considered related to the study intervention.• NOTE: An AE can therefore be any unfavorable and unintended sign (including an abnormal laboratory finding), symptom, or disease (new or exacerbated) temporally associated with the use of a study intervention.

Events Meeting the AE Definition

• Any abnormal laboratory test results (hematology, clinical chemistry, or urinalysis) or other safety assessments (e.g., ECG, radiological scans, vital signs measurements), including those that worsen from baseline, considered clinically significant in the medical and scientific judgment of the Investigator (e.g., not related to progression of underlying disease).• Exacerbation of a chronic or intermittent pre-existing condition including either an increase in frequency and/or intensity of the condition.• New conditions detected or diagnosed after study intervention administration even though it may have been present before the start of the study.• Signs, symptoms, or the clinical sequelae of a suspected drug-drug interaction.• Signs, symptoms, or the clinical sequelae of a suspected overdose of either study intervention or a concomitant medication. Overdose per se will not be reported as an AE/SAE unless it is an intentional overdose taken with possible suicidal/self-harming intent. Such overdoses should be reported regardless of sequelae.• "Lack of efficacy" or "failure of expected pharmacological action" per se will not be reported as an AE or SAE. Such instances will be captured in the efficacy assessments. However, the signs, symptoms, and/or clinical sequelae resulting from lack of efficacy will be reported as AE or SAE if they fulfill the definition of an AE or SAE.

Events NOT Meeting the AE Definition

- Any clinically significant abnormal laboratory findings or other abnormal safety assessments which are associated with the underlying disease, unless judged by the Investigator to be more severe than expected for the participant's condition.
- The disease/disorder being studied or expected progression, signs, or symptoms of the disease/disorder being studied, unless more severe than expected for the participant's condition.

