10.4.2 Definition of SAE

If an event is not an AE per definition above, then it cannot be an SAE even if serious conditions are met (e.g., hospitalization for signs/symptoms of the disease under study, death due to progression of disease).

An SAE is defined as any untoward medical occurrence that, at any dose:

a. Results in death

b. Is life-threatening

The term 'life-threatening' in the definition of 'serious' refers to an event in which the participant was at risk of death at the time of the event. It does not refer to an event, which hypothetically might have caused death, if it were more severe.

c. Requires inpatient hospitalization or prolongation of existing hospitalization (Applies only during the safety follow up period for participants who may have been discharged during the treatment period, ie, between Day 1 and Day 10)

- In general, hospitalization signifies that the participant has been detained (usually involving at least an overnight stay) at the hospital or emergency ward for observation and/or intervention that would not have been appropriate in the physician's office or outpatient setting. Complications that occur during hospitalization are considered AEs. If a complication prolongs hospitalization or fulfills any other serious criteria, the event is serious. When in doubt as to whether "hospitalization" occurred or was necessary, the AE should be considered serious.
- Hospitalization for elective intervention of a pre-existing condition that did not worsen from baseline is not considered an AE.

d. Results in persistent disability/incapacity

- The term disability means a substantial disruption of a person's ability to conduct normal life functions.
- This definition is not intended to include experiences of relatively minor medical significance such as uncomplicated headache, nausea, vomiting, diarrhea, influenza, and accidental trauma (e.g., sprained ankle) which may interfere with or prevent everyday life functions but do not constitute a substantial disruption.

e. Is a congenital anomaly/birth defect

f. Other situations

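### Whether COVID-19 progression to ventilation or high-flow oxygen is an AE/SAE is stated differently in section 7.1 and Appendix 4, leaving the SAE comparison dependent on which passage is followed

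*Protocol*

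**What the plan says.** The latest full text of the relevant sections is Version 2.0 (Amendment 1). The Version 3.0 change table lists only the Hy's law addition for section 7.1, plus minor language changes throughout, so item 3 appears unchanged, although its Version 3.0 wording is not shown.

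- **Section 7.1, item 3.** The item opens "AE/SAE if the Investigator believes that it is in best interest of the participant, including the following". Its list includes, without qualification, "Progressive COVID-19 requiring initiation of non-invasive or invasive ventilation or high flow oxygen".
- **Section 10.4.1 (Appendix 4).** Among events that do not meet the AE definition is "The disease/disorder being studied or expected progression, signs, or symptoms of the disease/disorder being studied, unless more severe than expected for the participant's condition". A separate bullet says that the "clinical sequelae resulting from lack of efficacy will be reported as AE or SAE if they fulfill the definition".
- **Section 10.4.2.** If an event is not an AE, "then it cannot be an SAE even if serious conditions are met"; death from disease progression is one of the examples given.
- **Section 8.3.6.** The disease-related events exempt from AE reporting are fever, cough, dyspnea, asthenia and loss of taste and smell. Respiratory failure and ventilation are not on the list.
- **Sections 8.3 and 8.3.2.** Both refer the reader to Appendix 4, for AE/SAE definitions and for the recording method respectively.
- **Section 9.4.5.1.** Participants with any SAE and any severe AE are counted, and "The number of deaths due to an AE, hospitalization due to an AE, and study discontinuation due to an AE will be summarized".
- **Section 9.1.** Level 5 (non-invasive ventilation or high-flow oxygen), level 6 (invasive ventilation or ECMO) and level 7 (death) form the primary composite. Section 9.2 plans for 15% on RESP301 and 30% on SOC, with 200 and 100 participants. Section 6.3 states that the study is open-label.

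**The concern.** The same intubation can be filed as an SAE by a site that follows 7.1, or left out of the AE record by a site that follows Appendix 4 and regards it as expected progression. The decision belongs to an investigator who knows the arm. Item 3 also concerns stopping study intervention, which controls do not receive, so its AE/SAE label comes into view more readily for RESP301 participants.

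SAEs and severe AEs are named safety endpoints in section 3, and section 9.2 has the IDMC assess safety at each interim analysis. If progression is counted, the SAE comparison partly restates the efficacy result and could mask harm from the inhalation. If it is counted unevenly, the comparison is biased. The recognised risks in Table 2-1 include bronchospasm and falling saturation, so respiratory events are where a clean comparison matters most.

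**Working it through.** **Planned figure.** Section 9.2 gives N = 300 for about 80% power, 30% vs 15%, 2:1, one-sided alpha 0.025. The pooled two-proportion formula with average rate (0.30 + 2 × 0.15)/3 = 0.20 gives 88 controls, N = 264. With continuity correction it gives 97 controls, N = 291 (98 and 294 at alpha 0.0249), and power at 100/200 of 81.3%. The stated figure therefore reproduces with the corrected formula, and the 15%, 30%, 200 and 100 can be used as the plan's own inputs.

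**Participants affected.** RESP301: 0.15 × 200 = 30. SOC: 0.30 × 100 = 30. Together 60 of 300.

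**What progression alone contributes to the SAE difference (RESP301 minus SOC).**
- Excluded in both arms: 0% - 0% = 0 points.
- Counted in both arms: 15% - 30% = -15 points (Fisher p = 0.003 for 30/200 vs 30/100).
- Counted in RESP301 only: 15% - 0% = +15 points.

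**Adding other SAEs.** The documents give no rate for other SAEs, so the rates below are assumptions. Taking them as independent of progression, the combined rate in an arm is p + (1 - p)x, with p the progression rate and x the rate of other SAEs. For x = 10% on RESP301 and 5% on SOC:
- RESP301: 0.15 + 0.85 × 0.10 = 0.235
- SOC: 0.30 + 0.70 × 0.05 = 0.335
- Difference: -10.0 points, SE = √(0.235 × 0.765/200 + 0.335 × 0.665/100) = 5.6 points

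| Other SAEs, RESP301 vs SOC (assumed) | Progression excluded in both | Counted in both | Counted in RESP301 only |
|---|---|---|---|
| 10% vs 10% | 0 | 23.5% vs 37.0%, -13.5 | 23.5% vs 10.0%, +13.5 |
| 10% vs 5% | +5.0 | 23.5% vs 33.5%, -10.0 | 23.5% vs 5.0%, +18.5 |
| 15% vs 10% | +5.0 | 27.75% vs 37.0%, -9.25 | 27.75% vs 10.0%, +17.75 |
| 15% vs 5% | +10.0 | 27.75% vs 33.5%, -5.75 | 27.75% vs 5.0%, +22.75 |

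**When one common rule reverses the sign.** The RESP301 rate of other SAEs must exceed the SOC rate x but stay below (0.15 + 0.70x)/0.85. At x = 5% that limit is 0.185/0.85 = 21.8%, an excess of up to 16.8 points. Over an assumed x of 2% to 20% the largest such excess runs from 17.3 down to 14.1 points. With no excess the difference is -15 × (1 - x), that is -14.7 points at x = 2% and -12.0 at x = 20%: it moves away from zero but does not reverse.

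**Limits of the count.** The planned rates cover levels 5 to 7 by Day 14, whereas item 3 covers levels 5 and 6, and the split is not given. A move to high-flow oxygen might be filed as a non-serious AE, which lowers the SAE count. Progression between Day 14 and Day 28 would raise it.

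**The case against.** The strongest reply is that the protocol does name a governing source. Sections 8.3 and 8.3.2 point to Appendix 4, and 7.1 is a stopping rule rather than a definition. Item 3 can then be read as covering only progression that is more severe than expected, which Appendix 4 accepts as an AE. This stands in part: Appendix 4 is the stated source, and it is not a flat exclusion. But item 3 carries no such qualification and does not refer to Appendix 4. The exception and the lack-of-efficacy bullet still leave each case to an unblinded judgement, with no statement of what progression is expected at level 4.

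Three further objections are sound. Section 7.1 does not class COVID-19 death as an AE/SAE, so for deaths it does not conflict with 10.4.2. The events are not lost, because the WHO level is recorded in both arms and progression and Day 28 mortality are efficacy endpoints that the IDMC can see. The layout of safety tables could also be left to the SAP. That last point does not dispose of the matter, because sites apply the reporting rule as events occur and an SAP cannot recover how inconsistently filed events should have been classified.

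A reader might infer that the plan's own rates are enough to reverse the SAE comparison. They are not: under one common rule a reversal needs an excess of other SAEs on RESP301, for which the documents give no rate. The route without that excess supposes different rules in the two arms, which no section prescribes.

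**Conclusion.** The inconsistency between 7.1 item 3 and Appendix 4 is real, and 8.3.6 does not settle it. It affects about 60 of 300 participants at the planned rates. Between excluding and counting progression in both arms, the SAE difference shifts by about 15 points in favour of RESP301 before overlap with other SAEs, and by 12 to 14.7 points if other SAEs run equally at 2% to 20% in each arm. These sizes assume that all progression events are treated alike within an arm, that each is serious when counted, and that progression and other SAEs are independent.

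Reversal is conditional. With assumed other SAEs of 10% vs 5%, the difference goes from +5 to -10 points; alternatively, the arms must be classified differently. What is affected is the interpretation of the SAE, severe-AE and AE-discontinuation tables. The primary endpoint and mortality are unaffected. The conclusion rests on item 3 being unchanged in Version 3.0, which the change table suggests but the available text cannot confirm.

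**What to change.** Reconcile 7.1 item 3 with 8.3.6, 10.4.1 and 10.4.2 so that a single AE/SAE classification of level >4 events applies identically in both arms. This can be done without altering when treatment stops and without introducing a new reporting rule. Making suspected relationship to study drug the only reporting route would not help, since that route is open mainly to the RESP301 arm.

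In 9.4.5.1, tabulate SAEs and severe AEs by arm in two ways: excluding COVID-19 progression events, and including every level >4 event and death taken from the modified WHO scale. List all deaths by arm regardless of AE status.

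The cost is wording in these sections, one extra pair of safety tables and a listing. The WHO level and deaths are already collected, so no new data are needed.
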